7.1.5. Adequate Baseline Tumor Assessment

Adequate baseline is defined using the following criteria:

- All baseline assessments must be within 28 days prior to and including the date of first dose.
- All documented lesions must have non-missing assessments (ie, non-missing measurements for target lesions and meeting criteria for measurable lesions, and non-missing lesions status at baseline for non-target lesions).
- Baseline lesions must be assessed with an acceptable method of tumor assessment as specified in the protocol (eg, Chest, abdomen, and pelvis CT scans [or CT without contrast or MRI if CT is contraindicated], an MRI of the brain, CT scan of the brain,

preferably with IV contrast, may be performed if MRI is contraindicated. Localized CT, MRI, or X-ray for skeletal lesions). Chest X-ray or ultrasound should not be used for tumor response assessments in this study. While FDG-PET scans are not required for this study, sites may perform combined PET/CT scans per their local standard of care, provided the CT is of similar diagnostic quality as CT performed without PET, including the use of oral and IV contrast media. If acquired according to local standard of care, FDG-PET may be relied upon to document PD in accordance with RECIST.

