7.2.2. Tumor Imaging During Screening

Initial tumor imaging must be performed within 28 days before the first dose of study treatment. Scans performed as part of routine clinical management are acceptable for use as the screening scan if they are of diagnostic quality and performed within 28 days before the first dose of study treatment.

The patient must have documentation of measurable disease per RECIST v1.1. Any lesions that have been subjected to loco-regional therapies (e.g., radiotherapy, ablation, etc.) should not be considered measurable, unless they have clearly progressed since the therapy. Previously treated lesions that have not progressed should be considered non-measurable and assessed as non-target lesions.

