7.5.1. Objective Response Rate

Objective Response (OR) based on IRR is the primary endpoint and is defined as CR or PR according to RECIST version 1.1 from date of first dose of study treatment until documented PD or start of new anticancer therapy. Both CR and PR must be confirmed by repeat assessments performed no less than 4 weeks after the criteria for response are first met.

Clinical deterioration or clinical progression noted on the End of Treatment Disposition eCRF will not be considered as documented disease progression for the purposes of the ORR calculation.

The confirmed BOR for each participant is determined from the sequence of overall time point (lesion responses) according to the following rules below:

- CR = at least 2 determinations of CR at least 4 weeks apart before progression.
- PR = at least 2 determinations of PR or better at least 4 weeks apart before progression (and not qualifying for a CR).
- SD = an assessment of SD or better ≥ 6 weeks after start of treatment (and not qualifying for PD, PR or CR).
- PD = progression ≤ 16 weeks after start of treatment (and not qualifying for CR, PR, or SD).
- NE (Not Evaluable) = all other cases (i.e. not qualifying for confirmed CR or PR and without SD after more than 6 weeks or early progression within the first 16 weeks).

Participants with a BOR of 'Not Evaluable' will be summarized by reason for having unknown status. The following reasons will be used:

- No adequate baseline assessment
- No evidence of disease at baseline
- No post-baseline assessments due to early death (defined as death prior to 6 weeks after date of first dose)
- No post-baseline assessment due to other reason
- All post-baseline assessments have overall response of "NE"
- New anticancer therapy started before first post-baseline assessment
- SD occurred < 6 weeks after the start of treatment and no subsequent tumor assessments

- Progression >16 weeks after the start of treatment (i.e., tumor assessment of PD was >16 weeks after start of treatment and there was no tumor assessment in between).

Special (and rare) cases where BOR is ‘Not evaluable’ due to both SD occurring < 6 weeks after start of treatment and progression > 16 weeks after the start of treatment will be classified as “SD occurred < 6 weeks after the start of treatment”.

The ORR will be calculated with the exact 2-sided Clopper-Pearson 95% CI.

A sensitivity analysis will be performed for ORR by IRR in RE set at the time of interim analysis.

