7.5.2. Duration of Response

DOR is defined as the time from the date of the first documented response (CR or PR) that is subsequently confirmed, to the earliest date of disease progression, as determined by IRR and investigator per RECIST v1.1, or death due to any cause. If a participant with a CR or PR has neither progressed nor died at the time of the analysis cutoff or at the start of any new anticancer therapy, the participant will be censored at the date of last adequate tumor assessment. The same rules used for censoring of PFS will be applied, see [Section 7.5.5](#) for more details. DOR will be calculated for participants who have achieved a confirmed response (i.e., CR or PR).

An estimate of the DOR survival function will be constructed using the KM method (Kaplan & Meier, 1958³) as implemented in PROC LIFETEST. The 25%, median, and 75% DOR (in months) will be summarized along with 95% confidence intervals as calculated from the PROC LIFETEST output (using method of [Brookmeyer & Crowley, 1982¹]).

Frequency distribution (<3 months, ≥3 months, ≥6 months, ≥9 months, ≥12 months, ≥24 months) will be provided.

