7.5.5. Progression-free Survival

Progression-free survival is defined as the time from the date of first dose of study drug to the earliest date of disease progression, as determined by IRR and investigator per RECIST v1.1, or death due to any cause, whichever occurs first, and will be summarized in months:

$$\text{PFS (months)} = [(\text{date of event or censoring} - \text{date of first dose}) + 1] / 30.4375.$$

Participants without an event or with an event more than 16 weeks (for the first 12 months after treatment start date) or 24 weeks (after the first 12 months of treatment start date) after the last adequate tumor assessment will be censored on the date of the last adequate tumor assessment that documented no progression. In addition, if a new anticancer therapy is started prior to an event, the participant will be censored on the date of the last adequate tumor assessment that documented no progression prior to the start of the new anticancer therapy. Note: if date of progression occurs on the same date as the start of new anticancer therapy, the progression will be counted as an event.

An adequate post-baseline assessment is defined as an assessment where a response of CR, PR, SD, non-CR/non-PD, or PD can be determined. Time points where the response is NE or no assessment was performed will not be used for determining the censoring date.

Participants with no baseline tumor assessment (including participants with an inadequate baseline assessment) or with no adequate post-baseline tumor assessments within 16 weeks after treatment start date will be censored on the day of treatment start date, unless the participant dies within 16 weeks of treatment start date, in which case, death will be an event on date of death.

The censoring and event date options to be considered for the PFS analysis are presented in Table 4.

Table 4. PFS Outcome and Event Dates

Situation	Date of Progression/Censoring	Outcome
No adequate baseline assessment	Date of treatment start date ^a	Censored ^a
PD or death ≤ 16 (or 24) ^b weeks after last adequate tumor assessment or ≤ 16 weeks after treatment start date	Date of PD or death	Event
PD or death > 16 (or 24) ^b weeks after the last adequate tumor assessment ^c	Date of last adequate tumor assessment ^c documenting no PD prior to new anticancer therapy or missed assessments	Censored
No PD		
New anticancer therapy given		

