10. APPENDIX 1: EVALUATION OF RECIST (VERSION 1.1) TUMOR ASSESSMENT CRITERIA

The primary efficacy analysis is based on IRR assessment per RECIST 1.1. The secondary efficacy analysis is based on derived investigator assessment of tumor data and confirmation of response is required.

This section describes the rules used for derivation of tumor response and progression based on derived investigator assessment of tumor data for secondary efficacy analyses.

Uses “start date” to denote the date of first dose of study drug.

SPECIFICATIONS FOR PROGRAMMATIC DERIVATION OF TUMOR RESPONSE USING RECIST 1.1

The primary efficacy analysis will be based on IRR interpretation of tumor assessment scans from study sites, performed by Bioclinica. The details of this process are described in the study specific Bioclinica charter. Analyses based on IRR will use data as transferred from IRR:

- BOR (but not the target response, non-target response and time point response at each time point) will be derived using the rules presented in this appendix.
- Date of progressive disease (PD) and determination of event or censoring for progression-free survival will be derived, from the PD date reported by IRR, the dates of time point tumor assessments reported by IRR and accounting for anticancer therapy and other censoring rules.

A secondary efficacy analysis will be based on a programmatic approach to derive tumor response/progression, using RECIST 1.1 and the investigator tumor assessment data recorded on the target, non-target, and new lesion eCRFs, as described below.

The tumor response criteria are based on RECIST 1.1 (Eisenhauer EA, Therasse P, Bogaerts J, et al. New response evaluation criteria in solid tumours: Revised RECIST guideline [Version 1.1]. *Eur J Cancer*. 2009;45(2):228-47).

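### SAP 7.5.2 carries the PFS rules that censor at treatment start into DOR, so a confirmed responder can have DOR censored before the response began

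*SAP*

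**What the plan says.** **Baseline adequacy.** SAP 7.1.5 requires that "All baseline assessments must be within 28 days prior to and including the date of first dose", that every documented lesion has a measurement or status, and that an acceptable imaging method was used. It does not say whether IRR's acceptance of a baseline settles the matter. SAP 7.1.6, by contrast, ties post-baseline adequacy to the response given by IRR or by the investigator.

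**Response.** SAP 7.5.1 defines "PR = at least 2 determinations of PR or better at least 4 weeks apart before progression", with no baseline condition. Not evaluable (NE) is what remains: "all other cases (i.e. not qualifying for confirmed CR or PR", and without qualifying stable disease or early progression. A list of reasons for NE follows, headed by "No adequate baseline assessment". In SAP Appendix 1, BOR for the IRR analysis "will be derived using the rules presented in this appendix"; Tables 12 and 13 there contain no baseline condition.

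**PFS.** SAP 7.5.5 opens one rule with "Participants with no baseline tumor assessment (including participants with an inadequate baseline assessment", adds those with no adequate post-baseline assessment within 16 weeks, and censors both groups at the treatment start date unless death occurs within 16 weeks. Table 4 (first row) and Table 5 (first in the hierarchy) repeat the baseline part.

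**DOR.** SAP 7.5.2 computes DOR for confirmed responders only. It counts progression or death as the event and censors event-free responders at the last adequate tumor assessment. It then adds: "The same rules used for censoring of PFS will be applied".

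**The concern.** DOR starts at the first response, and PFS starts at the first dose. Censoring at treatment start is a valid, if minimal, PFS time. For DOR it lies before the clock starts. Importing the PFS rules whole therefore gives a confirmed responder with a failed baseline an impossible duration, and removes a real progression if one follows.

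This matters because Protocol 4.2 rests the single-arm design on response rates that are durable as well as meaningful. The responders counted in ORR should be the same people whose durations are summarized. As written, two programmers could produce different DOR data sets from the same records, both following the SAP.

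**Working it through.** The plan gives no figure to reproduce here. The inputs are its own date rules.

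**Inputs**
- Duration in days = stop − start + 1, with 30.4375 days per month (SAP 7.1.9). The first dose is Day 1 (SAP 7.1.3).
- First scan 8 weeks after first dose, ± 7 days (Protocol 7.2.3): Day 56 + 1 = 57, range 50 to 64.
- Baseline window 28 days (SAP 7.1.5).

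**Worked case.** One baseline item is dated Day −35. IRR reports PR at Day 57 and again at Day 113, which is 56 days later and so satisfies the 4-week rule.

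1. *ORR:* confirmed PR, hence a responder. The NE category is not reached.
2. *PFS:* censored on Day 1, (0 + 1)/30.4375 = 0.03 months.
3. *DOR under the imported PFS rule:* 1 − 57 + 1 = −55 days, or −55/30.4375 = −1.81 months. Across the scan window: Day 50 gives −48 days (−1.58 months) and Day 64 gives −62 days (−2.04 months).
4. *If IRR reports progression at Week 40* (Day 40 × 7 + 1 = 281, an illustrative date, with scans up to date): the DOR definition gives an event at 281 − 57 + 1 = 225 days (7.39 months). The first row of Table 4 and the top of the Table 5 hierarchy give censoring on Day 1 instead.

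**Second route.** The 7.5.5 text also censors at treatment start when no adequate post-baseline assessment falls within 16 weeks. Sixteen weeks after first dose is Day 16 × 7 + 1 = 113, but the Week 16 scan may be done up to Day 120. If the Week 8 scan is missed or not evaluable and the first PR is at Day 120, later confirmed, the same rule gives 1 − 120 + 1 = −118 days (−3.88 months).

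**Does another rule catch this?** The negative-duration rule at the end of SAP 7.1.11 concerns imputed partial dates; the dates here are complete. The exception for death within 16 weeks rescues only a responder who dies that early. A negative time cannot enter a Kaplan-Meier estimate, and in the DOR frequency table in 7.5.2 it would fall in the band below 3 months unless excluded.

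**How many.** The documents give no rate of failed baselines. As an assumption, take 1% to 5%. At the design rates, responders number 60 × 0.65 = 39 and 37 × 0.45 = 16.65, so 0.39 to 1.95 treatment-naïve and 0.17 to 0.83 previously treated responders would be exposed by the baseline route, about 0.6 to 2.8 in all.

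**The case against.** **A sensible programmer would never do this.** The sentence just before the cross-reference already censors event-free responders at the last adequate assessment. The cross-reference can be read as bringing in only the missed-assessment and new-therapy rules. That is very probably the intent, and it stands as a reason to treat this as a drafting error. It does not remove the conflict. The cross-reference has no exception, and the preceding sentence covers only responders who have neither progressed nor died. For a responder who progresses, the DOR definition and the PFS hierarchy still disagree.

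**The case is rare.** Protocol 7.2.2 says "Initial tumor imaging must be performed within 28 days before the first dose of study treatment", and Protocol sections 5 and 7 allow no waivers. This stands and limits the size of the point. Missing lesion data and late first scans are further routes, also uncommon.

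**The PFS rule is deliberate.** It is consistent between the 7.5.5 text and Tables 4 and 5, has a stated exception for early death, and its censored participants are counted by reason. Loosening it in an open-label study whose current SAP followed an interim analysis would be a debatable change. This stands.

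**A stronger reading to avoid.** A reader might infer that the NE reason headed "No adequate baseline assessment" turns confirmed responders into failures, with a loss of power for the primary test. The text does not support that. NE is reached only by participants who lack a confirmed response, and the list classifies participants already in it. The response evaluable set in SAP 5.3 does require an adequate baseline, so the response analyses are not silent on the matter, but that set serves only a sensitivity analysis of ORR at the interim. One reservation is that SAP 10.4.1 also refers to an Oncology Rulebook, and Appendix 1 to an imaging charter. Neither is available here.

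**Conclusion.** The DOR censoring rule is wrong as written. Followed literally, it gives a confirmed responder with a failed baseline a duration of about −1.6 to −2.0 months when the response is at the first scheduled scan, or discards a later progression. It conflicts with both the event definition and the censoring sentence in SAP 7.5.2.

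The effect is confined to DOR, a secondary endpoint, by IRR and by investigator alike. It probably concerns between none and about three responders; that range rests on an assumed 1% to 5% of failed baselines. The primary ORR count, its rejection rules and their power are unaffected on the supplied text. The documents do not support a finding against the PFS baseline rule itself.

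**What to change.** 1. In SAP 7.5.2, state that the parts of 7.5.5 and Tables 4 and 5 that censor at the treatment start date do not apply to DOR. For confirmed responders, progression or death is an event, subject to the missed-assessment and new-therapy rules; otherwise DOR is censored at the last adequate assessment on or after first response.
2. In SAP 7.5.1, add that the NE reasons classify only participants whose BOR is already NE and do not override a confirmed CR or PR.
3. Leave the PFS baseline rule, including its exception for death within 16 weeks, as prespecified. Optionally add a sensitivity PFS analysis that keeps participants whose baseline IRR accepted.

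The cost is two sentences of SAP text and a minor programming change. A simple check follows: confirmation comes at least 28 days after first response, so a correctly derived DOR should be at least 28 + 1 = 29 days, and the number of participants in the DOR analysis should equal the number of confirmed responders.

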7.1.6. Adequate Postbaseline Tumor Assessment

An adequate assessment is defined as an assessment where a response of CR, PR, Stable Disease (SD), non-CR/non-PD (to be used if only non-measurable disease is present), or PD has been provided by IRR or the investigator for the analyses by IRR or investigator, respectively. Time points where the response is not evaluable or no assessment was performed will not be used for determining the censoring date for time to event endpoints.

7.1.7. Definition of Start of New Anticancer Therapy

Start date of new anticancer therapy (drug, radiation, surgery) is used for censoring in efficacy analyses (see [Section 7.5](#)).

The start date of new anticancer therapy is the earliest date after first dose date among the following:

- Start date of anticancer drug therapy recorded in the ‘Subsequent Cancer Treatment Systemic’ eCRF pages;
- Start date of radiation therapy recorded in ‘Subsequent Cancer Treatment Radiation’ eCRF pages;
- Surgery date recorded in ‘Subsequent Cancer Treatment Surgery’ eCRF pages;

When start date of anticancer therapy is missing or partially missing, the imputation rules described in [Section 7.1.11](#) should be applied using ‘Subsequent Cancer Treatment Systemic’, ‘Subsequent Cancer Treatment Radiation’, and ‘Subsequent Cancer Treatment Surgery’ eCRF pages.

7.1.8. Tumor assessment dates

Tumor assessment dates will be assigned differently for IRR assessment and for investigator’s assessment of tumor data.

For analyses of IRR assessments, the date of tumor assessments will be provided by IRR and identified as the earliest scan/assessment date at each nominal timepoint. These dates, together with the determined overall tumor response at each timepoint, will be used to programmatically identify the response/progression date and for censoring in time to event analyses.

For analyses based on investigator's assessment, response/progression are derived programmatically from the target lesions measurements, non-target lesions status, and new lesions recorded on the eCRF, and the date of tumor assessment will be derived as the earliest scan/assessment date.

7.1.9. Reporting Conventions

Unless specified otherwise, durations of events (e.g., duration of treatment) will be calculated in days as (stop date – start date + 1).

The following conversion factors will be used to convert days into weeks, months or years:

$$1 \text{ week} = 7 \text{ days}, 1 \text{ month} = 30.4375 \text{ days}, 1 \text{ year} = 365.25 \text{ days}.$$

Demographics and physical measurements:

- Age (years):
 - (date of given informed consent - date of birth + 1) / 365.25
 - In case of only year and month given: (year/month of given informed consent – year/month of birth)
 - In case only year of birth is given: (year of given informed consent – year of birth)
 - The integer part of the calculated age will be used for reporting purposes.

For each analysis, a data cutoff date will be determined. Only data with an assessment/finding dates (eg, vital sign assessment date, tumor scan date, laboratory collection date, etc) or event/intervention start date (eg, AE start date, concomitant medication start date) before or on the cutoff date will be included in the analysis.

All events with a start date before or on the cutoff date and an end date after the cutoff date will be considered as continuing at the cutoff date. The same rule will be applied to events starting before or on the cutoff date and not having a documented end date. Participants with a last contact date or a date of death after the data cutoff date will be considered alive at the data cutoff date. Participants known to be on treatment or discontinued the treatment after the cutoff date will be considered on treatment at the time of data cutoff date.

In general, missing values will be handled as follows unless otherwise specified. For continuous variables at baseline, missing values will be excluded from calculation of summary statistics, and the number and percent of participants with missing values will be displayed. For categorical values at baseline, the number and percent of participants with a missing value will be displayed. For missing post-baseline values, the method for reporting missing values will depend on the summary table.

Qualitative/categorical data will be summarized by frequency counts and percentages. Percentages will be calculated using the number of participants or subgroup as the denominator. Continuous data will be summarized using appropriate descriptive statistics (e.g. mean, standard deviation, median, minimum, and maximum).

For reporting conventions, minimum and maximum values will be presented with the same decimal precision as collected in the raw data; mean, median, and quartiles should generally be presented to one more decimal place than the raw data; standard deviation should be displayed to two more decimal places than the raw data. Percentages will be reported to one decimal place. Unless otherwise noted, for all percentages, the number of participants in the analysis set who have an observation will be the denominator.

Data listings will be sorted by participant identifier, parameter, and the corresponding date of assessment. The listing source will be included in the footer of the listings.

7.1.10. Unscheduled Visits

Generally, data collected at unscheduled visits will be included and analyzed for both safety and non-safety analyses in the same fashion as the data collected at scheduled visits except where otherwise noted in the sections that follow. Descriptive statistics (mean, standard deviation, median, minimum, maximum, quartiles) by nominal visit or time point for safety endpoints such as laboratory test measurements, ECGs, and vital signs will not display data from unscheduled visits/assessments.

